4.3 Interim analyses and data monitoring

No interim analysis is planned for this study. No Data Monitoring Committee will be established for this study.

4.4 Multicenter studies

Individual center results will not be directly presented. Centers are only located in North America and Europe.

4.5 Multiple comparisons/multiplicity

Not applicable.

4.6 Use of an efficacy subset of subjects

Not applicable.

4.7 Active-control studies intended to show equivalence

Not applicable.

4.8 Examination of subgroups

Not applicable.

4.9 Additional study-specific information

The subjects of DV0004 are ongoing subjects of PA0012. Data cut off for the final analysis in DV0004 will be after the follow-up of the last subject. Data cut off rules will be applied for ongoing ADEs and ongoing concomitant medication, such that any ADE or concomitant medication which has no stop date, or a stop date after the data cut off for DV0004 will be assigned as “Ongoing”.

A number of parameters in the PA0012 and DV0004 studies have the potential to break the blinding of the feeder study treatment allocations. In order to safeguard against unscheduled unblinding of the PA0010 and PA0011 studies before their respective database locks, a blinding maintenance plan will be developed and implemented for DV0004 and PA0012. This will ensure both PA0012 & DV0004 remain blinded to feeder study treatment allocation, until after both feeder studies have been unblinded. This plan will document in detail how the DV0004 Data Evaluation Meetings and final delivery will be handled prior to Feeder Study unblinding.

4.9.1 COVID-19 category definition

The coronavirus disease of 2019 (COVID-19) pandemic was declared by the WHO on 11 March 2020. The worldwide pandemic restricted travel and had potential impact on ongoing clinical trials. The following definitions will be used to present pre-specified summaries:

- *Pre-pandemic*: Events or assessments occurring before 11-Mar-2020
- *During pandemic*: Events or assessments occurring on or after 11-Mar-2020

A post-pandemic definition is not applicable to this short study.

5 STUDY POPULATION CHARACTERISTICS

5.1 Subject disposition

The disposition of subjects including the number of subjects in ES and all device-specific analysis sets (SS-s, FAS-s, PK-PPS-s or SS-a, FAS-a, PK-PPS-a) will be summarized. This summary will be based on ES and will present subjects overall and by site and country/region (North America/Europe).

The number and percentage of subjects who entered the substudy, completed, discontinued with the reasons for discontinuation of the substudy will be presented. This summary will be based on the ES and will present all bimekizumab treated subjects broken out by DV0004 device group.

The following listings for subject disposition will be produced based on the ES and presented by DV0004 device group:

- A listing of subjects who did not meet the eligibility criteria
- A listing of subject disposition
- A listing of discontinuation
- A listing of visit dates
- A listing of subjects excluded from analysis sets
- A listing of subject analysis sets

5.1.1 Impact of COVID-19 on subject disposition

Subject disposition will also be summarized by COVID-19 enrollment period (pre- and during-pandemic), as defined in Section 4.9.1. The number of completed, missed and partial visits will be presented by COVID-19 enrollment period.

5.2 Protocol deviations

A summary of number and percentage of subjects with an important protocol deviation (including a summary of subjects excluded from any analysis set due to important protocol deviations) by DV0004 device group will be provided for the SS-s and SS-a. A summary of COVID-19 related important device protocol deviations will be presented by visit for the SS-s and SS-a. COVID-19 related important protocol deviations will be identified by the prefix of “COVID” in the deviation verbatim text.

By-subject listings of important protocol deviations and COVID-related important device protocol deviations will be provided separately.

5.3 Impact of COVID-19

The impact of the COVID-19 pandemic on study procedures and conduct, such as missed/remote visits, interruption of study treatment, will be documented using the information collected on a dedicated eCRF page. The number and percentage of subjects impacted by COVID-19 will be presented overall and by country.

A by-subject listing of the impact of COVID-19 on study visits will be provided.

6 DEMOGRAPHICS AND OTHER BASELINE CHARACTERISTICS

All summaries detailed in this section will be performed on the SS-a and SS-s. Demographics and other baseline characteristics will be extracted from the Feeder Study Baseline data.

6.1 Demographics

The following continuous variables will be summarized using descriptive statistics (number of subjects, mean, standard deviation (SD), minimum, median and maximum).

- Age at the time of Feeder Study entry (years)
- Height at Feeder Study Baseline (cm)
- Weight (kg) at DV0004 Baseline: This will be derived from the weight from the last visit of the feeder study or DV0004 Entry Visit, since these visits will occur on the same day and weight is only collected once
- DV0004 Baseline BMI (kg/m²)

BMI (kg/m²) will be calculated as:

$$BMI = \frac{\text{Weight (kg) at DV0004 Baseline}}{[\text{Height (m) at Feeder Study Baseline}]^2}$$

The following categorical variables will be summarized using frequency counts and percentages:

- Age group (≤ 18 , $19 < 65$, ≥ 65 years)
- Body Weight at DV0004 Baseline (≤ 100 kg, > 100 kg)
- BMI (< 25 kg/m², 25 to < 30 kg/m², ≥ 30 kg/m²)
- BMI tertiles ($\leq t1$ kg/m², $> t1$ kg/m² to $\leq t2$ kg/m², $> t2$ kg/m²) based on the respective PK populations (PK-PPS-s, PK-PPS-a)
- Gender
- Race
- Ethnicity
- Country

By-subject listings of demographics will be provided.

Demographics will also be summarized by COVID-19 enrollment period (pre- and during-pandemic), as defined in Section 4.9.1.

6.2 Other Baseline characteristics

Generally, the following continuous variables will be summarized using descriptive statistics (number of subjects, mean, SD, minimum, median and maximum):

- Duration of disease (years)

Duration of disease (years) will be calculated as:

$$\text{Disease duration} = \frac{(\text{Date of randomization in DV0004} - \text{Date of onset of PsA}^1)}{365.25}$$

¹ If the date of onset of PsA is partial, it should be imputed to the most recent feasible date (i.e., last day of the month if only day is missing, or last day of the year if day and month are missing).

Baseline characteristics will also be summarized by COVID-19 enrollment period (pre- and during-pandemic), as defined in Section 4.9.1.

6.3 Medical history and concomitant diseases

Previous and ongoing medical history from the feeder study will be based on SS-s and SS-a and summarized by system organ class (SOC) and preferred term (PT) using MedDRA[®]. Medical procedures are not coded.

Previous and ongoing medical history will be presented in a by-subject listing for SS-s and SS-a, respectively.

All medical conditions not yet occurred and reported in the feeder studies will be presented in a table and a by-subject listing for SS-s and SS-a, respectively.

6.4 Prior and concomitant medications

Concomitant medication details are collected at each visit of DV0004. Concomitant medications are medications taken with at least one day in common with the DV0004 study medication dosing period (DV0004 Baseline to DV0004 Week 4).

Imputation of missing start and stop dates are described in Section 4.2.

All concomitant medication will be listed for SS-s and SS-a, respectively.

Concomitant medication which started before DV0004 Week 4 and were ongoing at the data cut off will be included with the status remaining as ongoing. Concomitant medication which were ongoing at DV0004 Week 4 but with an end date before the data cut off will be included with their end date as recorded.

7 MEASUREMENTS OF TREATMENT COMPLIANCE

During the Treatment Period of this study, IMP administration (either self-administration or study personnel-administration) will be performed in the clinic and observed by the Investigator or his/her designee; monitoring subject compliance is therefore not applicable.

8 EFFICACY ANALYSES

No efficacy summaries are planned for the DV0004 substudy.

9 PHARMACOKINETICS AND PHARMACODYNAMICS

9.1 Pharmacokinetics

The statistical analyses of the PK data will be descriptive in nature and will be summarized using the relevant device presentation-specific population (PK-PPS-s or PK-PPS-a). Data will be analyzed overall for each device presentation by injection type (self-administered or study personnel-administered), by injection site (abdomen or thigh), by anti-bimekizumab antibody visit status, and by BMI category. Three BMI categories will be defined based on tertiles derived from subjects' DV0004 Baseline BMI values. See Section 9.2 for details on classification of anti-bimekizumab antibody status.

To allow for an analysis of bimekizumab PK trough levels, blood samples will be taken before self-injection using the assigned self-injecting device presentation at the DV0004 Baseline Visit

and DV0004 Week 4 (Visit 2), and before injection by site personnel at PA0012 Week 8 (Visit 3 of PA0012).

PK samples at DV0004 baseline will be summarized under administration by site personnel (since the previous dose was given by site personnel). PK samples associated with self-administration (at Week 4 and Week 8), but where the previous injection was done by site personnel or care-giver, will be listed but not be used for summary statistics.

Only pre-dose (trough) concentrations will be included while summarizing tables and figures. If the dosing for a visit is +/- 7 days out of window, then the plasma concentration from that visit will be excluded from the PK summary. PK samples are expected to be collected prior to dosing. PK samples collected >14 days after the preceding dose and no later than 1 hour after the current dose will be included in the summary. PK samples collected later than 1 hour after dosing will be excluded from summary statistics. PK results at visits following a previous non-dosing visit will be excluded from summary statistics.

PK summaries will be based on observed values. No imputation will be used. However, if plasma concentration measurements are below the level of quantification, then for calculation of the derived statistics the result will be set to ½ of the lower level of quantification (LLOQ). Descriptive statistics including the geometric mean, geometric coefficient of variation, and geometric mean 95% confidence interval (CI) if applicable will be calculated if at least ⅓ of the values of interest are above the LLOQ. If this is not the case, only median, minimum, and maximum will be presented. Time from previous bimekizumab dose to DV0004 visit will be summarized by device presentation.

A minimum of 3 values are required to calculate summary statistics. If only 2 values are available, then these should be presented as the minimum and maximum with other descriptive statistics reported as missing.

Boxplots and summaries of plasma concentration will be presented by visit, by device presentation, and by cumulative ADA_b status considering DV0004 alone and considering DV0004 and the feeder studies (see Section 9.2). Cumulative ADA_b status is defined in Section 9.2. Boxplots and summaries of plasma concentration will be presented by visit, by device presentation and by injection site, and by BMI tertile.

All PK results will be listed. Baseline PK samples are the PK samples prior to first dose of Bimekizumab at DV0004 entry visit.

In addition, the PK results from all subjects not in PK-PPS-s or PK-PPS-a will be listed based on the SS-a and SS-s. All concentrations will be listed as received, prior to any substitution of BLQ and LLOQ values. The listing will include flags for concentration that were excluded from the summary statistics, with the reason for exclusion.

9.2 Immunogenicity

The immunological variable is anti-bimekizumab antibodies (ADA_b) evaluated at DV0004 Baseline and Week 4, and PA0012 Week 8 visits. To allow for an analysis of ADA_b, blood samples will be taken before self-injection at the DV0004 Baseline Visit and DV0004 Week 4 (Visit 2), and before injection by site personnel at PA0012 Week 8 (Visit 3 of PA0012). ADA_b

status at or prior to the PK sampling (at DV0004 Baseline, DV0004 Week 4, and PA0012 Week 8) will be used in the summaries.

The ADA_b will be assessed using a 3-tiered assay approach: Screening, confirmatory, and titration assays. Screening, confirmatory and titer cut points of the respective assays will be determined by the bioanalytical laboratory. The relevant statistical reports will be provided as part of the bioanalytical reports.

The Screening cut point will be used to determine the ADA_b status in the test sample as “Positive Screen” (PS) or “Negative Screen” (NS). For samples presenting anti-BKZ antibody levels that are PS, further confirmatory assay will be performed, and the result of which will be reported as either “Positive Immunodepletion” (PI) or “Negative Immunodepletion” (NI).

Positive immunodepletion samples will be titrated, and the ADA_b titer (reciprocal dilution factor including minimum required dilution [MRD]) reported.

ADA_b status for each visit will be derived as follows:

- Sample values that are either NS or PS and NI, and where the BKZ concentration is less than the validated ADA_b assay drug tolerance limit (200 µg/mL), will be defined as **ADA_b negative**.
- Sample values that are either NS or PS and NI and where the BKZ concentration exceeds the validated ADA_b assay drug tolerance limit (200 µg/mL) will be defined as **inconclusive**.
- Sample values that are PS and PI will be defined as **ADA_b positive** (regardless whether a titer is available or not)
- Missing if it does not go into one of the above categories.

If a sample is collected within 21 days (inclusive) before or after the visit date at which the drug was administered, the ADA_b results for that sample will be associated with the scheduled visit and summarized accordingly. Samples collected outside this window will be excluded from the by-visit ADA_b summaries and figures and will be listed only. This window will not apply to the summary of cumulative ADA_b status, all available data will be used to derive the cumulative ADA_b status.

The number and percentage of ADA_b-positive and ADA_b-negative subjects before self-injection (DV0004 Baseline) and after self-injection (at DV0004 Week 4 and PA0012 Week 8) will be summarized by visit. The ADA_b visit status will be based on the confirmatory assay at the respective visit. This visit status and the overall status (considering data in DV0004 only and data in DV0004 and the feeder studies) will be used for the summary tables and will be based on the Safety Set.

Cumulative ADA_b status is used for the box plots and summaries described in Section 9.1.

Cumulative and overall ADA_b status is derived as follows:

a. Considering data in DV0004 only:

- If a subject is ADA_b positive at any time during DV0004 up to and including the respective DV0004 visit, they are assigned ADA_b cumulative positive status for that and all subsequent

visits. This will be based on the confirmatory assay at each visit in DV0004 (Baseline, Week 4, Week 8).

- If a subject has only negative ADA_b samples or only one missing/inconclusive sample with all negative ADA_b samples up to that timepoint, the subject will be classified as negative.
 - Otherwise, the study participant will be classified in the missing ADA_b category.
- b. Considering data in the feeder studies (PA0010, PA00011) and DV0004:
- If a subject is ADA_b positive at any time in PA0010/PA0011 and DV0004 up to and including the respective DV0004 visit, they are assigned ADA_b cumulative positive status for that and all subsequent visits. This will be based on the cumulative status at DV0004 Entry Visit (last visit in Feeder Study) and the confirmatory assay results in DV0004 (Week 4 and Week 8).
 - If a subject has only negative ADA_b samples or only one missing/inconclusive sample with all negative ADA_b samples up to that timepoint, the subject will be classified as negative.
 - Otherwise, the study participant will be classified in the missing ADA_b category.

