14.10 Determination of sample size

This study will not be powered with respect to any endpoint, and sample size is based on practical considerations. In order to maintain blinding in the PA0012 feeder studies (PA0010 and PA0011), DV0004 will recruit all subjects who complete the PA0010 and PA0011 feeder studies (including those treated with a comparator or placebo in the feeder study) up to a total of about 200 subjects. A total of 100 subjects (50 subjects per device presentation arm) are planned for PK trough level analyses, but these analyses will only be performed on subjects who were treated with bimekizumab 160mg Q4W (ie, not with placebo or comparator) in the feeder studies prior to rolling over into the DV0004 substudy. The DV0004 substudy will enroll approximately 200 subjects (to compensate for subjects treated with placebo or comparator) to ensure that 100 subjects with stable (160mg Q4W bimekizumab) PK trough levels are available for PK trough analysis.

Subjects who enroll in the DV0004 substudy will be randomly assigned to the bimekizumab-SS-1mL or the bimekizumab-AI-1mL device presentation arms (each device presentation arm will consist of approximately 100 subjects). Within each device presentation arm, subjects will be divided into tertiles by BMI: there will be approximately 33 subjects per tertile, which is expected to yield approximately 16 to 17 subjects per tertile who are evaluable for steady state trough PK level analyses.

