3.4.2 Safety Set

Two different Safety Sets (SS) will be generated (1 for each device presentation): the bimekizumab-SS-1mL Safety Set (SS-s) and the bimekizumab-AI-1mL Safety Set (SS-a). Each SS will consist of all subjects in the study who receive at least 1 dose of bimekizumab by the indicated self-injecting device presentations. Safety variables will be analyzed using the SS-s and SS-a.

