3.4.4 Pharmacokinetic Per Protocol Set

Two different Pharmacokinetic Per Protocol Sets (PK-PPS) will be generated (1 for each device presentation): the bimekizumab-SS-1mL PK-PPS (PK-PPS-s) and the bimekizumab-AI-1mL PK-PPS (PK-PPS-a). Each PK-PPS will consist of all subjects who receive the same bimekizumab administration (frequency and dose) in the PA0012 feeder studies as in the DV0004 substudy and who have at least 1 evaluable PK assessment in the DV0004 substudy without important protocol deviations that would affect the concentration. Pharmacokinetic variables will be analyzed using the PK-PPS-s and PK-PPS-a.

All PK assessments after baseline assessments from the feeder study will be considered for the one evaluable PK assessment.

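### The before/after self-injection ADAb tables pool all feeder treatments, so Baseline may mix bimekizumab exposure histories and part of any rise may come from subjects starting the drug

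*SAP*

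**What the plan says.** SAP 9.2 summarizes ADAb status by visit, with DV0004 Baseline as the time before self-injection and Week 4 and PA0012 Week 8 as the times after it. Both the visit status and the overall status "will be used for the summary tables and will be based on the Safety Set".

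SAP 3.4.2 defines each device's Safety Set as "all subjects in the study who receive at least 1 dose of bimekizumab by the indicated self-injecting device presentations". There is no condition on feeder treatment. SAP 3.5 states that the treatment grouping takes no account of what was received in the feeder study, and SAP 4.8 plans no subgroups.

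Protocol 14.10 recruits feeder completers, "including those treated with a comparator or placebo in the feeder study", up to about 200. It gives the reason for that number as "to compensate for subjects treated with placebo or comparator": 100 subjects (50 per device arm) with bimekizumab 160 mg Q4W in the feeder study are wanted for the trough analyses.

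For pharmacokinetics the plan does restrict the population. Under SAP 3.4.4 the PK Per Protocol Set (PK-PPS) is limited to "all subjects who receive the same bimekizumab administration (frequency and dose) in the PA0012 feeder studies as in the DV0004 substudy", with further conditions on evaluable samples and deviations. No section applies that restriction, or a split by feeder treatment, to the ADAb incidence tables.

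The immunogenicity objective (Protocol 3.3, SAP 2.1.3) names two things: self-injection with the devices, and injection by study personnel with the 1 mL PFS.

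**The concern.** Baseline is the only DV0004 sampling time that can speak to the PFS half of the objective, because the Week 4 and Week 8 samples follow device injections. For a subject who had bimekizumab by PFS in the feeder study, the Baseline sample does that. For a subject who had none, it follows no bimekizumab dose at all. A column that pools both kinds of subject reports a mixture, and the PFS part cannot be read off it.

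The same mixture affects the before/after reading. A subject who starts bimekizumab in DV0004 may become ADAb positive because exposure has begun, whatever the device. The table sets a time before self-injection beside times after it, so a pooled rise invites a device explanation that it may not deserve.

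At stake is the interpretation of one descriptive variable, which is among the other objectives of the study.

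**Working it through.** **The plan's own counts.** Protocol 14.10 gives about 200 subjects, 100 per arm, with 100 (50 per arm) for the trough analyses. These agree with each other: 50/100 = 50%; 200 x 0.5 = 100; 100/3 = 33.3 per BMI tertile (stated: about 33); 50/3 = 16.7 (stated: 16 to 17).

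**Two shares to keep apart.**
- g = share of a device's Safety Set outside the group that had bimekizumab 160 mg Q4W in the feeder study. On the planning counts g is about (100 - 50)/100 = 0.5. The 50 is a target for PK-evaluable subjects, so the true g may differ.
- f = share with no prior bimekizumab at all. Such subjects are all outside the same-regimen group, so f cannot exceed g, and g may exceed f. The documents do not say whether any subject in the other group had bimekizumab earlier. From the planning counts, f could be anything from 0 to about 0.5.

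**Rise with no device effect.** Let b and q be the ADAb prevalence in the f group before and after starting bimekizumab, and hold everyone else's rate constant. The pooled rise is f x (q - b). The documents give no ADAb rates; b = 2% and q = 5%, 10% or 20% are assumptions.

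| f | q = 5% | q = 10% | q = 20% |
|---|---|---|---|
| 0 | 0 | 0 | 0 |
| 0.05 | 0.05 x 3 = 0.15 | 0.05 x 8 = 0.4 | 0.05 x 18 = 0.9 |
| 0.2 | 0.2 x 3 = 0.6 | 0.2 x 8 = 1.6 | 0.2 x 18 = 3.6 |
| 0.5 | 0.5 x 3 = 1.5 | 0.5 x 8 = 4.0 | 0.5 x 18 = 9.0 |

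The entries are percentage points, which in an arm of 100 are also subjects. Other assumed rates change the size but not the direction: with b = 5%, q = 10-30% and f = 0.5, the rise is 0.5 x 5 = 2.5 to 0.5 x 25 = 12.5 points.

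**Dilution of Baseline.** Let p be the ADAb rate at Baseline in subjects with prior bimekizumab (assumed equal across feeder regimens). The pooled Baseline is (1 - f) x p + f x b, with b = 2%.

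| f | p = 10% | p = 30% |
|---|---|---|
| 0 | 10.0% | 30.0% |
| 0.05 | 9.6% | 28.6% |
| 0.2 | 8.4% | 24.4% |
| 0.5 | 6.0% | 16.0% |

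**Whether another output already shows this.**
- SAP 5.1 summarizes "The disposition of subjects including the number of subjects in ES and all device-specific analysis sets", and SAP 5.2 adds deviation counts, "including a summary of subjects excluded from any analysis set due to important protocol deviations". The gap between Safety Set and PK-PPS gives a rough bound on the mix, but it also contains same-regimen subjects without an evaluable sample.
- SAP 9.1 analyses PK-PPS concentrations by antibody "visit status, and by BMI category", and summarizes them by cumulative ADAb status. The number in each category gives ADAb counts only for same-regimen subjects whose concentration is summarized.
- The overall status in SAP 9.2 that adds feeder data lengthens the history used for each subject. It does not change who is in the table.

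**The case against.** The strongest reply is that the plan claims nothing that the table cannot bear. SAP 9.2 labels Baseline only as the time before self-injection; it never calls the Baseline ADAb rate a PFS result. The link from the Baseline sample to injection by personnel is made for PK (Protocol 5.1 and 14.4, SAP 9.1), where the population is restricted. The analysis is descriptive throughout, with no device/PFS contrast. ADAb in everyone who used a device is a legitimate summary, and ADAb arising after device injection in a previously untreated subject is a real finding. The concentration summaries by ADAb status already give part of the same-regimen picture, and subject data will be listed. A split would still leave time on drug confounded with before/after.

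Most of this stands, and it is why the Safety Set total should stay and the point is minor. It does not answer the gap against the objective, which names PFS injection and is served by no ADAb incidence table that isolates it.

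Four stronger readings are tempting, and the documents support none of them:
- That the pooled Baseline says nothing about PFS injection. About half of the planned subjects had bimekizumab 160 mg Q4W in the feeder study, so the column is diluted, not empty.
- That about half of each arm had no prior bimekizumab. The planning counts identify who was on the same regimen, not who was untreated. The artefact could be zero.
- That Baseline follows PFS injection only in the same-regimen group. Any other subject who had bimekizumab by PFS in the feeder study would be a counterexample.
- That the SAP changed the ADAb population without declaring it. Protocol 14.4 places the ADAb summary in a section that uses the PK sets, but names those sets for the PK data. Extending them to ADAb is a reading, not a stated rule.

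**Conclusion.** The concern holds in a limited form. The ADAb tables ignore feeder treatment in a study that deliberately enrols mixed feeder treatments. Their Baseline column may therefore mix exposure histories, and part of any pooled rise may come from subjects starting bimekizumab.

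The size is unknown. Under the main assumed rates (2% before, 5-20% after starting), it runs from nothing at f = 0 to 1.5-9.0 points at f = 0.5. Both f and the rates are assumptions; only the planned 100 of about 200 is documented.

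Severity is minor. The tables describe one of the other variables, and no primary or secondary result depends on them. This is a cheap improvement, not a correction of an error.

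**What to change.** In SAP 9.2, keep the Safety Set total. Add, within each device group and after both feeder studies are unblinded, the by-visit and overall ADAb tables split by feeder treatment actually received:

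- (a) bimekizumab 160 mg Q4W;
- (b) other feeder treatment, showing any subjects with prior bimekizumab separately from those whose feeder data confirm none.

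Report the number of subjects per feeder treatment among the Baseline characteristics in SAP 6.2. State that Baseline is read as following PFS injection of bimekizumab only for subjects whose feeder data show bimekizumab given by PFS. Add a footnote that time on drug still confounds before and after in every column, so no device effect should be inferred.

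The cost is SAP wording and a column split on existing data. The blinding arrangement in SAP 4.9 is no obstacle once both feeder studies are unblinded. The downside is precision. Using the exact 90% interval from SAP 3.1 and an assumed 30% positive, 30/100 gives 22.5-38.4% and 15/50 gives 19.5-42.4%. Small parts of (b) would be wide: 5/50 gives 4.0-19.9%, and 1/20 gives 0.3-21.6%.
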